8.6 Un-blinding Process

In the event of an emergency PI or medically qualified delegate can request unblinding from the dispensing team.

The a member of the research team will notify the CI in writing as soon as possible following the code break detailing the necessity of the code break. Given that the nature of the placebo and supplement, where the supplement is a commercially available supplement that will be taken within the recommended daily doses and that the participants will all be healthy volunteers it is not anticipated that any emergencies will arise as a direct consequence of consumption of either the placebo or the fish oil supplement. Therefore 24h unblinding is not required.

The PI must document the breaking of the code and the reasons for doing so on the CRF/data collection tool in the site file and medical notes. All unblinding will also be documented at the end of the study in any final study report.

At the end of the trial once all the analysis has been conducted the codes will be broken by the CI.

8.7 Experimental Methods

After collection samples will be processed William Harvey Centre for Biochemical Pharmacology/Clinical Pharmacology Laboratories within one hour of following standard operating procedures listed in the *Lipid Mediator Unit Laboratory Manual*.

White Blood cell phagocytosis of Escherichia coli:

- 20 µl of blood will be incubated with 2×10^7 C.F.U. of fluorescently labeled E. coli

- Cells will be incubated at 37°C for 1h
- Cells will then be processed for flow cytometry using established protocols
- The extent of phagocytosis will be assessed using flow cytometry

Peripheral blood cell activation

- 20µl of whole blood will be incubated with or without 100µM of PAF for 1h at 37°C
- Cells will be washed 2x with PBS containing 5% fetal calf serum
- Cells will then be incubated with the following fluorescently conjugated antibodies for 15 min at room temperature
- Cells will then be processed for flow cytometry
- Adhesion molecule expression as well as platelet-leukocyte aggregates will be assessed using flow cytometry

Lipid mediator profiling

- Plasma (2ml) will be placed in 8 ml of ice-cold methanol containing deuterium labeled internal standards
- Samples will be stored at temperatures of -80°C
- Samples will be processed in batches of 20-24.
- Here samples will be centrifuged at 3000xg for 10 min at 4°C
- Supernatants will be collected
- Lipid mediators (LM) will be extracted using solid phase extraction techniques
- Isolated LM will be profiled using liquid chromatography tandem mass spectrometry (see ref 17)
- At the end of the study any excess or unused samples will be disposed of unless written consent is obtained from participant for longer term storage. Sample disposal will be conducted following standard operating procedures as outlined in the Biochemical Pharmacology laboratory manual.

RNA storage

If participant consent, blood will also be collected and stored in RNA stabilizing reagent for later processing. These samples will be used to assess the expression of genes involved in the initiation and resolution of inflammation. This sample collection will be conducted with the understanding that the participants will not be informed of any genetic information, and that the team dealing with them in the trials unit will also never be made aware of any genotyping information (a one-way donation). These samples will be stored for a maximum of 2 years. RNA will be used to investigate the expression of SPM biosynthetic enzymes, the SPM receptors and pathways that these molecules may activate.

8.8 Clinical Protocol

At least 24h prior to consent, participants will be provided an information sheet by an appropriate method including email, post or by attending the clinic, detailing the rationale and hypothesis of the study and on attending the screening visit the study physician will address any questions that the participants may have. They will be asked to sign the informed consent and then their eligibility criteria will be assessed based on the inclusion criteria set out for the study. Basic observations, blood pressure, pulse, resting supine ECG, Blood samples for full blood count, biochemistry and glucose and CRP, then a physical examination will be performed.

Volunteers passing screening will then:

- Will give a baseline blood sample (12ml)
- Be given one of the randomly allocated three doses of fish oil supplement, or a matching placebo [this will be on a 1:1:1:1 ratio].
- Give blood (12ml/time interval) will be collected again at 2h, 4h, 6h
- Be allowed to leave and they will be asked to return the following day for the collection of the 24h blood sample.
- Be asked to return after a minimum of 48h but no later than 2 weeks
- Identity will be verified
- Blood will be obtained (12ml)
- Be given the next supplement dose/placebo that is listed on their assigned study group and the injection witnessed by a member of the study team.
- Blood will be obtained after 2h, 4h and 6h.
- Be free to leave and will be asked to return after 23h from supplementation
- The 24h blood sample will be collected and the participants will be asked to return again after a minimum of 48h and no later than 2 weeks for their next supplement dose/placebo cycle
- Identity will be verified
- Blood will be collected (12ml)
- Supplement/placebo will be administered and ingestion witnessed.
- Blood will be collected at the same intervals outlined above
- Participants will be asked to return for the last supplement dose/placebo listed on their study group at least 48h after the last blood donation (24h blood sample) but no later than 2 weeks.
- Essentially the same protocol outlined above will be followed for the last cycle.
- A first follow-up phone-call to the volunteer will be made to check well-being at 2 weeks (+/- 1 week) after the end of the volunteers last cycle
- A Second follow-up phone-call to the volunteer will be made to check well-being at 4 weeks (+/- 1 week) after the end of the volunteers last cycle

Participants can withdraw from the study at any time.

8.9 Schedule of Assessment (in Diagrammatic Format)

Assessment	Screening	Study Visit 1 (Week 1)	Study Visit 2 (Week 1+24h)	Study Visit 3 (Week 2)	Study Visit 4 (Week 2+24h)	Study Visit 1 (Week 3)	Study Visit 2 (Week 3+24h)	Study Visit 3 (Week 4)	Study Visit 4 (Week 4+24h)	Follow up telephone call	End of Study telephone call
Informed written consent Inclusion/Exclusion criteria	x										
ID Assessment using Photo id	x	x	x	x	x	x	x	x	x		
Weight	x										
Height	x										
Screening bloods*	x										
Pregnancy test	x										
Resting ECG	x										
Physical examination	x										
Assess adverse events		x	x	x	x	x	x	x	x	x	x
Dosing		x		x		x		x			
Document any medication	x	x		x		x		x			
Blood draw** @ 0hrs		x		x		x		x			
Blood draw @ 2hrs		x		x		x		x			
Blood draw @ 4hrs		x		x		x		x			
Blood draw @ 6hrs		x		x		x		x			
Blood draw @ 24hrs			x		x		x		x		

8.10 End of Study Definition

The CI is delegated the responsibility of submitting the EOT notification to REC once reviewed by sponsor. The EOT notification must be received by REC and within 90 days of the end of the trial.

If the study is ended prematurely, the Chief Investigator will notify the Sponsor & REC including the reasons for the premature termination (within 15 days).

The trial will end after the last healthy volunteer's last visit and the analysis of all sample analysis has been completed.

8.11 Subject Withdrawal

PI may/must withdraw participants from the study if during any point they intake any medication, alcohol, other supplements or oily fish prior to the last blood draw (24h). If participants are not able to make their next visit within the stipulate window (2 weeks + 48h from the supplement/placebo dose) they will be re-screened prior to re-enrolling.

If blood cannot be obtained at the 0h, 2h, 4h or 6h time intervals then the participant will be withdrawn from the primary analysis. If the blood cannot be withdrawn at the 24h interval the participant can still be included for primary and secondary endpoint analysis.

If a participant is withdrawn from the study they may re-enroll in the study after being >14 days free of medication.

If the participant withdraws before the completion of the 4th visit and dosing of supplement/placebo the samples and information will be still be analysed, but the study analysis will be primarily by per-protocol (complete treatment cycles only), although all data will also be analysed for Intention-to-treat as a secondary analysis.

Withdrawn subjects may be replaced at the discretion of the investigator.

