7.4 Study Design / Plan – Study Visits

This is an open label double-blind, placebo controlled, crossover study that aims to determine the dose of omega-3 fatty acids that leads to an increase in peripheral blood SPM levels and the kinetics of this regulation.

- Each participant will give a baseline blood sample then they will be given one of the randomly allocated three doses of fish oil supplement, or a matching placebo in one of 8 study groups [this will be on a 1:1:1:1:1:1:1:1 ratio]. Blood will be collected again at 2h, 4h, 6h and 24h after supplementation/placebo.

- This design allows to compare the levels of SPM pre and post supplementation and therefore to account for inter participant variation in circulating SPM levels as well as for any differences in white blood cell responses *ex vivo*.

- Using a crossover design and a placebo, diurnal variation in the levels of SPM (currently not known) will be checked. In addition, using each volunteer as their own control for comparison with each dose of supplement will further improve the power of the study.

- Each participant is expected to be involved in the study for a maximum of 11 weeks from initial consent and screening.

- Participants will be asked to refrain from consuming caffeine containing drinks at least 2h prior to their visit.

- Participants will be expected to refrain from alcohol intake for at least 24h before screening for the study, and for at least 24h before each cycle of the study.

- Participants will also be asked not to take other supplements, medications for the duration of the study, and to avoid fish containing meals for 2 days before each study cycle.

- For each cycle, the participants will make two visits, the first visit will be of a maximum of 8hrs. Here baseline (0hrs) blood sample will be obtained and the supplement/placebo given.

- Blood will be collected 2hrs, 4hrs and 6hrs following supplement/placebo intake and the participant will be free to leave after the 6hrs blood collection.

- During this time participants will be asked to refrain from drinking caffeine containing drinks such as coffee or tea.

- Participants will then be asked to return the next day (24h after fish oil supplement/placebo intake).

[figure not shown]
- The 24h blood draw should take a maximum of 30 min.

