8.3 Intervention

After determining eligibility participants will be randomly assigned to one of the eight groups outlined in the table below where each participant will receive all three doses and the placebo but in a different sequence to minimise any interaction effects.

In order to ensure adequate recruitment into all eight cycles prior to interim analysis group allocation will be divided into two blocks with 20 volunteers per block. Each of the supplement capsule contains 1.5g of essential fatty acids. So administration of 1 supplement capsule and 2 placebo capsules will deliver 1.5g of omega-3 fatty acids, administration of 2 supplement capsules and 1 placebo capsule will deliver 3 g of omega-3 essential fatty acids and administration of 3 supplement capsule will deliver 4.5g essential fatty acids.

Group	Treatment			
	Cycle 1	Cycle 2	Cycle 3	Cycle 4
Group 1	3 capsules Placebo	1 capsules Supplement & 2 capsules Placebo	2 capsules Supplement & 1 capsules Placebo	3 capsules Supplement
Group 2	1 capsules Supplement & 2 capsules Placebo	2 capsules Supplement & 1 capsules Placebo	3 capsules Supplement	3 capsules Placebo
Group 3	2 capsules Supplement & 1 doses Placebo	3 capsules Supplement	3 capsules Placebo	1 capsules Supplement & 2 capsules Placebo
Group 4	3 capsules Supplement	3 capsules Placebo	1 capsules Supplement & 2 capsules Placebo	2 capsules Supplement & 1 capsules Placebo
Group 5	3 capsules Supplement	2 capsules Supplement & 1 capsules Placebo	1 capsules IMP & 2 capsules Placebo	3 capsules Placebo
Group 6	2 capsules Supplement & 1 capsules Placebo	1 capsules Supplement & 2 capsules Placebo	3 capsules Placebo	3 capsules Supplement
Group 7	1 capsules Supplement & 2 capsules Placebo	3 capsules Placebo	3 capsules Supplement	2 capsules Supplement & 1 capsules Placebo
Group 8	3 capsules Placebo	3 capsules Supplement	2 capsules Supplement & 1 capsules Placebo	1 capsules Supplement & 2 capsules Placebo

This above protocol will be followed until all forty participants are recruited (unless halted after the interim analysis).

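### Section 8.11, read literally, drops all four of a participant's cycles from the primary analysis for one missed 0h–6h draw; the paired tests do not need this, and the per-protocol sentence beside it is ambiguous

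*Combined protocol and SAP*

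**What the plan says.** Section 8.3 makes this a four-period crossover: "each participant will receive all three doses and the placebo but in a different sequence". Section 7.4 takes a baseline sample in each cycle and then continues: "Blood will be collected again at 2h, 4h, 6h and 24h after supplementation/placebo". The schedule in 8.9 confirms draws at 0h, 2h, 4h and 6h in all four cycles.

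Section 8.11 then contains two rules that bear on the primary analysis set.

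- Missed draws: "If blood cannot be obtained at the 0h, 2h, 4h or 6h time intervals then the participant will be withdrawn from the primary analysis". Only the last draw is exempt: "If the blood cannot be withdrawn at the 24h interval the participant can still be included for primary and secondary endpoint analysis".
- Early leavers: "If the participant withdraws before the completion of the 4th visit and dosing of supplement/placebo the samples and information will be still be analysed". The same sentence then sets against this a limit on which data are primary: "the study analysis will be primarily by per-protocol (complete treatment cycles only". An intention-to-treat analysis of all data is secondary.

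The same section lets withdrawn participants re-enrol under a condition and adds: "Withdrawn subjects may be replaced at the discretion of the investigator".

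Section 9.3 asks for 33 participants and names 2h and 4h as the times compared with pre-supplementation values. Section 9.4 plans a Wilcoxon matched-pairs signed rank test of each post value against the same person's pre-test value, and no comparison between times.

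**The concern.** In the missed-draw rule the unit is the participant, a single miss is enough, and no words confine the loss to the cycle in which it happened. A volunteer who completes four cycles but fails to give one tube would contribute nothing to the primary analysis. Each planned comparison uses two samples, so most of what is discarded could have been analysed.

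The per-protocol sentence does not resolve this. If it refers to single dosing periods, someone who stops after one complete cycle keeps it, while someone who finishes all four and misses one tube keeps none. If it refers to the whole sequence, both are excluded and the two rules agree. The text supports either reading, so two analysts could build different primary sets from the same data.

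At stake is the margin of 40 − 33 = 7. It must also absorb early leavers and withdrawals for medication, alcohol, supplements or oily fish.

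**Working it through.** **Inputs.** 40 participants (8.3); 33 required, threefold odds of an increase, 80% power, 5% level (9.3); four cycles (8.3); four mandatory draws per cycle at 0h, 2h, 4h and 6h (8.9, 8.11). The documents give no rate of missed draws.

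**1. The plan's own figure.** Threefold odds means P(increase) = 3/(1+3) = 0.75. The two-sided sign-type formula gives n = (1.960 + 0.842)² / (4 × 0.25²) = 31.4, so 32. Dividing by the Wilcoxon relative efficiency of 0.955 gives 32.9, so 33. The figure is therefore reproducible. The formula behind it cannot be confirmed, because reference 18 in the list is a rat diet study and sidedness is not stated. The 33 applies to one pre/post comparison, so the relevant count is participants contributing a pair at a given dose and time.

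**2. What one miss costs.** Section 9.4 does not say which baseline is used; with a 0h sample in every cycle, the natural choice is that cycle's own. Pairs per participant are then:

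- 3 post-dose times × 4 cycles = 12 if 6h is analysed. A missed post-dose draw loses 1, and the literal rule discards the other 11.
- 2 × 4 = 8 if only 2h and 4h are analysed. A missed 6h draw loses none, and the literal rule discards all 8.
- A missed 0h draw loses that cycle's pairs (3 of 12, or 2 of 8) but none from the other three cycles.

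**3. Count with no assumed rate.** Mandatory draws: 4 × 4 × 40 = 640. Eight misses in eight different people are 8/640 = 1.25% and leave 40 − 8 = 32, below 33. If only the affected cycle is dropped, 8 of 40 × 4 = 160 cycles go, on average 8/4 = 2 per treatment, leaving about 38. It would be 32 only if all eight fell on one treatment.

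**4. Illustration with an assumed rate.** With independent misses at rate m per draw and no replacement, expected n = 40 × (1 − m)^k, where k = 16 under the literal rule and k = 4 at cycle level.

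| m | literal rule | cycle level |
|---|---|---|
| 0.5% | 36.9 | 39.2 |
| 1% | 34.1 | 38.4 |
| 2% | 29.0 | 36.9 |
| 5% | 17.6 | 32.6 |

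The break-even rate for 33 is m = 1 − (33/40)^(1/k): 1.20% for k = 16 and 4.70% for k = 4. Under the sign-type formula, power = Φ(0.5√n − 1.960). This gives 81.9% at 33, 76.7% at 28.95 and 85.9% at 36.89 (the unrounded values at 2%).

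**5. Clustering.** If misses concentrate in the same people (beta-binomial, m = 2%), literal and cycle-level n are 33.0 and 37.3 at within-person correlation 0.1, and 34.8 and 37.6 at 0.2.

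**6. Use of the word cycle.** The visit bullets in 7.4 (two visits per cycle) and the column heads of the 8.3 table use it for one dosing period. The return-visit bullet in 7.4 (the next dose within the cycle), the text of 8.3 (eight cycles, meaning the eight groups) and 12.1 (the cycle a participant is enrolled to) use it for the whole sequence.

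**The case against.** The strongest reply is that 8.11 can be read consistently. Early leavers' samples are analysed, but the primary analysis is per-protocol; that contrast suggests early leavers fall outside the primary set, with completers primary and all data secondary. This stands. A reader might infer that the two rules flatly contradict each other, but step 6 shows that the documents do not support so firm a claim. What remains is an undefined term, and a missed-draw rule stricter than the test needs on either reading.

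Second, a completers-only set has value: the same people appear at every dose and time, which helps because 9.3 picks a dose and time by greatest change and 9.4 picks a time by counting significant results. This partly stands. A cycle-level rule keeps the same people across times within a dose, so the choice of time is unaffected; n can differ slightly between doses.

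Third, the loss may be small. A reader might infer that the trial will end up underpowered. The documents give no miss rate, replacement and re-enrolment are allowed, and clustering at 0.1 leaves the literal-rule n at about 33. The secondary analysis uses all data, and the synopsis calls the study exploratory with no formal analysis. These points limit the impact, but replacement is discretionary and the secondary analysis does not repair the primary set.

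Finally, one might infer that 6h has no place in the primary analysis. That is not established either: 9.4 refers to each time point, and 7.4 aims at "peripheral blood SPM levels and the kinetics of this regulation". Its role is simply unstated.

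**Conclusion.** The point holds as a combination of over-strictness and ambiguity. Followed as written, the missed-draw rule discards usable pairs from up to three complete cycles for one missing tube, and it makes 6h mandatory without 9.3 or 9.4 saying that 6h is analysed. Whether it also conflicts with the per-protocol sentence depends on the meaning of cycle.

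The margin over 33 is exhausted at about 1.2% missed draws under the literal rule and 4.7% at cycle level. Both figures assume independent misses, 40 enrolled, no replacement and no other losses. The 2% row is illustrative only. The waste of usable data does not depend on any rate; the effect on power does. Priority is minor to moderate.

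**What to change.** - Reword the missed-draw rule in 8.11, for example: *If a sample required for the primary analysis is missing, that cycle is excluded from the primary analysis; the participant's other cycles are kept.*
- Define a complete treatment cycle as one dosing period and use that unit in the per-protocol sentence.
- State in 9.3 and 9.4 whether 6h belongs to the primary analysis, and make the list of required draws in 8.11 match.
- Report n for each dose. As a sensitivity analysis, repeat the choice of dose in participants with all four cycles complete.
- Keep the planned Wilcoxon test.

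The cost is a few sentences, with no extra samples or visits. The downside is slightly unequal n between doses, which the last reporting step addresses. The wording should be settled before any data are analysed, including at the interim analysis mentioned in 8.3, so that the primary set is not chosen after seeing results.

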9. STATISTICAL CONSIDERATIONS

9.1 Primary Endpoint

The Primary endpoint of the study will be an increase in peripheral blood SPM levels that will be measured using established liquid chromatography tandem mass spectrometry based approach.

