5.3 Fish oil supplementation to boost endogenous SPM

Evidence that chronic inflammation may result from inability of the body to produce adequate levels of SPM to counter regulate the ongoing inflammation suggests that increasing endogenous omega-3 levels may help promote SPM formation and thereby facilitate the termination of inflammation. A Pubmed search for the term 'fish oils supplementation + inflammation' yielded over 500 hits highlighting the fact that Fish oil supplementation is of general interest to both the academic and clinical fields and has been extensively studied. Animal studies using both fish oil as the main source of omega-3 essential fatty acids as well as other omega-3 enriched supplements

provide further evidence for the relationship between increased SPM production following supplementation and a reduction in inflammation (17-19). Studies with humans also indicate that fish oil supplementation may exert protective actions in chronic conditions such as rheumatoid arthritis (20) and certain cardiovascular diseases (21).

Omega-3 essential fatty acid supplementation has also been associated with increase SPM production in humans. In healthy volunteers taking 4 g of fish oil per day for three weeks plasma levels of three SPM, RvD1, RvD2 and AT-RvD1 were found to increase (22). In a separate study patients with chronic kidney disease were given 4 g of essential fatty acids and the investigators found significant increases in markers SPM pathways and RvD1 (23). In patients diagnosed with Alzheimer's or minor cognitive impairment, omega-3 fatty acid supplementation improved or stabilized cognitive function, it also lead to an increased ability of peripheral blood monocyte derived macrophages to phagocytose Amyloid β , and increase RvD1 levels (24). We recently developed a new platform that allows for the simultaneous measurement of all the pro-resolving mediators in addition to their pathway markers (>90 molecules) in human tissues. Using this platform we found that supplementation of healthy volunteers of healthy volunteers with 1 g essential fatty acids and aspirin increased plasma SPM levels, including RvD1, RvD2, RvD5 and RvE2 ((25), as early as 4 hours after intake providing the first evidence in humans that omega-3 supplementation can rapidly increases plasma SPM levels.

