5.5 Rationale for choice of doses

Given that in a study using a different fish oil source and formulation we found that 1 g of essential fatty acids gave a mild but significant increase in plasma SPM levels (25) we chose the lowest dose in the study to be of 1.5g. We then chose to investigate two other doses that were within the **European Food Safety Authority's Tolerable Upper Intake Level for supplements containing both EPA and DHA (See Appendix 2 and 3)**. Given that this limit is of 5 g and previous study with both healthy volunteers and patients demonstrated that doses up to 4 g are well tolerated (22-24), we chose the remaining 2 doses to be 3.0 g and 4.5 g. In addition, this supplement was awarded a **Generally Recognized as Safe Status (see appendix 1)** in the for a dose of up to 5 g. Similar doses of the emulsion from of the fish oil supplement are also being used in an ongoing clinical study in the USA (ClinicalTrials.gov Identifier: NCT02719665) measuring different outcomes to those being investigated in the present study.

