9.3 Sample Size

Power calculations were conducted using data obtained from published studies where healthy volunteers were given 1 mg essentially (from a different source to that being investigated in the present study) and peripheral blood lipid mediator levels were evaluated pre-essential fatty acid and 4 hours after supplement intake (Colas et al Reference 17). Using pre and post values of 10 mediators values from these studies and Wilcoxon matched-pairs signed rank test a sample size of 33 participants is required to detect a threefold odds of an increase in post value when compared with the pre value with a power of 80% at the 5% level of statistical significance using the formulae from reference 18. Fifty mediators will be examined and it is recognized that at the 5% level of statistical significance around 2-3 mediators will falsely be identified as having significant changes. However the functional effect of all significant mediators will be subsequently examined by assessing white blood cell function, including the ability of peripheral white blood cells to phagocytose bacteria and the response of peripheral white blood cells and platelets to an inflammatory stimulus. If we do not observe increases in the ability of peripheral white blood cells to phagocytose bacteria and/or decreases in the activation of peripheral white blood cells and platelets then these mediators will be assumed to be false positive results. For these analysis the white blood cell function and peripheral blood lipid mediator levels at the 2h and 4h intervals post essential fatty acid/placebo administration will be compared to pre-supplementation values. The time point and dose that give the greatest change in all the mediators and the greatest regulation of peripheral white blood responses will be judged to be the main outcome measure for future trials.

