9.4 Statistical Analysis Plan

Wilcoxon matched-pairs signed rank test will be used to analyse the pre and post values of 10 mediators as well as white blood cell function (at 2 and 4h). The time point corresponding to the greatest number of the mediators being statistically significantly different from their pre-test values at the 5% level of statistical significance will be identified as the time point of interest. At the 5% level of significance testing 50 mediators will result in at least 2-3 associations being falsely statistically significant. Thus, the functional effect of all significant mediators will be subsequently examined by assessing white blood cell function, including the ability of peripheral white blood cells to phagocytose bacteria and the response of peripheral white blood cells and platelets to an inflammatory stimulus to determine if the identified associations are likely to be true changes. If we do not observe increases in the ability of peripheral white blood cells to phagocytose bacteria and/or decreases in the activation of peripheral white blood cells and platelets then these mediators will be assumed to be false positive results. Values at different times will not be compared just the value at each time point will be compared to the same person's pre test values.

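### The plan declares one primary endpoint, an increase in blood SPM levels, but no rule or primary contrast says which of its many mediator results would meet it

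*Combined protocol and SAP*

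**What the plan says.** Sections 6.3 and 9.1 of the combined protocol and SAP word the primary endpoint as one outcome: "The Primary endpoint of the study will be an increase in peripheral blood SPM levels". Neither names a mediator or total, a dose, a time or a comparator.

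The other sections bearing on it are these:

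- **Mediators.** Section 9.4 says "Wilcoxon matched-pairs signed rank test will be used to analyse the pre and post values of 10 mediators". Section 9.3 says "Fifty mediators will be examined", and 9.4 also uses 50 when it counts expected false positives. Section 5.3 describes a platform for "simultaneous measurement of all the pro-resolving mediators in addition to their pathway markers (>90 molecules").
- **Doses.** The lowest dose is 1.5 g, and section 5.5 adds "we chose the remaining 2 doses to be 3.0 g and 4.5 g". With placebo, each participant has four cycles. Section 7.4 says the study "aims to determine the dose of omega-3 fatty acids that leads to an increase in peripheral blood SPM levels", but no dose comparison is primary and no order of testing is given.
- **Times.** Section 7.4 says "Blood will be collected again at 2h, 4h, 6h and 24h after supplementation/placebo". The tests in 9.3 and 9.4 use 2h and 4h, each against pre-dose. The sample size rests on earlier data "evaluated pre-essential fatty acid and 4 hours after supplement intake", but 9.4 does not make 4h primary.
- **Selection rules.** Section 9.4 takes as the time of interest the one with most mediators significantly different from pre-dose; the direction of the difference is not specified. Section 9.3 selects the dose and time with the greatest change, as the outcome measure for later trials.
- **Cell-function check.** Under 9.3 and 9.4, significant mediators are treated as false positives unless phagocytosis rises and/or cell activation falls.
- **Status.** The synopsis calls the study exploratory and says no formal statistical analysis will be done.

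**The concern.** A primary endpoint should be something the data can meet or fail to meet. Here the analysis yields a grid of p-values by mediator, dose and time, and nothing maps that grid to the statement that SPM levels rose. The plan does not say how many mediators must rise, at which dose or time, or what follows if some rise and others fall.

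Several readings are reasonable: any mediator up, most mediators up, or a summary measure up. If they can disagree on the same data, the conclusion depends on a choice made after the results are seen. Adjusting the individual p-values would not cure this, because a rule linking the adjusted results to the endpoint would still be missing.

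**Working it through.** **1. The plan's own figures.** Threefold odds of an increase (9.3) gives p = 3/(1+3) = 0.75, so (p − 0.5)² = 0.0625.

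- Signed-rank (Noether) formula, N = (z_α + z_β)² / [3(p − 0.5)²]. One-sided 5%, 80% power: (1.645 + 0.842)² / 0.1875 = 6.18 / 0.1875 = 32.97, so 33. Two-sided: 7.85 / 0.1875 = 41.9, so 42.
- Sign-test form, N = (z_α + z_β)² / [4(p − 0.5)²]. Two-sided: 7.85 / 0.25 = 31.4, so 32.

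The stated 33 is therefore reproduced, as the size for one pre/post comparison; 9.3 does not state sidedness. The expected false positives also reproduce: 50 × 0.05 = 2.5.

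**2. How many tests the plan allows.** Mediators × active doses × times: 10 × 3 × 2 = 60, or 50 × 3 × 2 = 300. The sample size covers one.

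**3. False increases at one dose and time, no true effect.** A two-sided 5% test gives a false increase with probability 0.025. If mediators are independent, the chance of at least one is 1 − 0.975^10 = 22.4% for 10 mediators and 1 − 0.975^50 = 71.8% for 50.

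Real mediators are probably correlated, so this was also simulated: n=40 (the planned number), equicorrelated normal within-person changes, Wilcoxon signed-rank tests, increases only. The correlations are assumptions.

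| Reading of the endpoint | Correlation 0.5 | Correlation 0 |
|---|---|---|
| One summary (mean across mediators) | 2-3% | 2-3% |
| Any of 10 mediators up | about 15% | about 23% |
| Any of 50 mediators up | about 32-35% | about 71-73% |

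Repeat runs for 10 mediators at correlation 0.5 ranged from 13% to 16%.

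**4. All three doses and both times, no true effect.** With correlation 0.8 down to 0, any mediator up at any dose or time occurred in 40% to 75% of trials (10 mediators) and 62% to 100% (50). The summed mediators at one fixed dose and time were up in about 2-3%.

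**5. Do readings disagree on the same data?** Assume a 0.3 SD shift in every mediator, correlation 0.5, one dose and time. 'Any up' was positive in 89% of trials (10 mediators) and 98% (50); 'majority up' was positive in 39% and 38%. The two disagreed in 49% and 59% of trials. The disagreement shrinks if every mediator shifts strongly, since both readings are then usually positive.

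**6. Does a single summary cost or gain power?** Under the Noether reading, the plan's effect is about 0.48 SD for normal changes. With n=40 and correlation 0.5:

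| Mediators responding at 0.48 SD | Summary | At least one mediator after Bonferroni |
|---|---|---|
| All | 97-98% | 92% |
| 20% | about 12% | 67-73% |

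The answer depends on how many mediators respond, which the documents do not say.

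**7. The cell-function check.** It was not simulated, because it has no threshold. It is worded as and/or, and does not say which dose, or which of the two times, the cell result must come from. One cell-function result is shared by all significant mediators, so it keeps or discards them together. It cannot confirm individual mediators or say when the endpoint is met.

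**The case against.** The strongest reply is that the study is exploratory. The synopsis says so, 9.3 openly expects 2-3 false positives, and the selected dose and time are meant for future trials. On that view a decision rule is a reviewer's preference. This stands in part: the harm is mainly to how a declared primary result can be reported. It does not dispose of the point, because section 9 also sets a primary endpoint, 80% power, a named test and a 5% level, and section 8.11 refers to a primary analysis. The two positions need reconciling.

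The second reply is that the plan does more than pick a time. It has a dose-and-time selection rule and a cell-function check. A reader might infer that one rising mediator at one dose and time is enough to claim success, or that the 15-73% above is the plan's own false-positive rate. The documents support neither. A significant mediator must still pass the check, and the percentages describe particular readings before a check that is too loosely defined to model. What remains is that neither the selection rule nor the check defines success.

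A reader might also infer that a single summary would be more powerful. That holds only if most mediators respond. Section 5.3 reports earlier rises mediator by mediator (including RvD1, RvD2, RvD5 and RvE2), so a partial response is plausible and the advantage could reverse sharply.

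**Conclusion.** The point holds: the plan has no success rule and no primary contrast for its single declared endpoint, so the same data could be reported as positive or negative. With no true effect at one dose and time, the chance of a false increase runs from about 2-3% to about 73% depending on the reading. Under an assumed 0.3 SD shift in all mediators, two plausible readings disagree in about half of trials. These sizes rest on n=40, normal equicorrelated changes, correlations of 0 to 0.5 and no cell-function check. The absence of a rule rests on the text alone.

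The figure of 33 is not in error for a single comparison. The exploratory label makes this a change the sponsor should make rather than a fatal flaw.

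**What to change.** Before the code is broken, amend 9.1 and 9.4 as follows.

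1. **One primary variable per participant and cycle.** List an SPM set drawn from the families in 5.2 (D- and E-series resolvins, protectins, maresins). Combine it on a stated scale, such as the mean of log or standardised values; in a raw sum abundant mediators could dominate.
2. **One primary contrast.** Use the 0h-to-4h change in the active cycle minus the same participant's 0h-to-4h change in the placebo cycle. The sample size uses 4h. Section 7.4 includes placebo because diurnal variation in SPM is unknown, so a within-cycle test alone could mistake a diurnal rise for an effect.
3. **One decision rule.** Test the three doses at two-sided 5% in a pre-stated order, stopping at the first non-significant result. Call the endpoint met only if the first test shows an increase.
4. **Labels.** Make individual mediators and other times secondary or exploratory, settle 10 versus 50, and reconcile the synopsis with section 9.

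The cost is SAP wording; the 0h and 4h samples are already scheduled in all four cycles (8.9). There are three downsides:

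- Power for the primary test is low if only a minority of mediators respond (about 12% if 20% respond at 0.48 SD, before placebo subtraction). Such rises would be reported as exploratory.
- Later doses in the order cannot be claimed if the first test fails.
- The sample size should be rechecked for the new contrast. If changes in the two cycles were independent with equal variance, subtraction would double the variance, and 0.48 SD would become 0.48/√2 = 0.34 SD. Positive within-person correlation would soften this.
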